- ⁱ A sweat chloride test must be performed at the Screening Visit if an eligible sweat chloride value is not available in the subject's medical records and the Screening Visit value is needed to establish eligibility. For subjects using sweat chloride values documented in their medical records to establish eligibility, the sweat chloride test at the Screening Visit is optional.

Table 3-2 Study VX15-661-112: Treatment Period (Day 1 to Week 72), Early Termination of Treatment Visit, and Safety Follow-up Visit Assessments

Event/Assessment ^a	Day 1	Day 15 (± 3 days)	Week 4, Week 12, (± 1 week)	Week 24 (± 1 week)	Week 36, Week 48, Week 60 (± 1 week)	Week 72 (± 1 week)	Early Termination of Treatment Visit (Within 7 days After Last Dose of Study Drug)	Safety Follow-up Visit 4 weeks (± 7 days) After Last Dose of Study Drug ^b
Clinic visit	X	X	X	X	X	X	X	X
Inclusion and exclusion criteria review ^c	X							
Randomization ^d	X							
Complete physical examination ^f	X					X	X	X
Pregnancy test ^g	urine		urine	urine	urine	urine	serum	serum

^a All assessments will be performed before dosing unless noted otherwise. If study drug is not administered on the day of the visit (i.e., study drug interruption or premature discontinuation of study drug treatment), only 1 set of assessments will be collected.

^b The Safety Follow-up Visit is not required for subjects who complete the Week 72 Visit and have enrolled in the TEZ/IVA open-label extension study, VX14-661-110, within 28 days after the last dose of study drug.

^c The screening inclusion and exclusion criteria should be re-reviewed before administration of study drug on Day 1.

^d Randomization must occur after the informed consent/assent has been obtained and all inclusion and exclusion criteria are met and before the first dose of study drug. Randomization will be done through an interactive web response system. Randomization may occur on Day -1 if the above conditions for randomization have been met.

[figure not shown]
^f In addition to the indicated visits, a symptom-targeted physical examinations will occur at any time during the study if triggered by adverse events (AEs) or if deemed necessary by the investigator.

^g Pregnancy tests will be performed for all female subjects of childbearing potential. Day 1 results will be reviewed before dosing and the Low-dose CT scan. Week 72 results will be reviewed before the Low-dose CT scan.

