6. At the Week 72 Visit, the morning dose of study drug will NOT be administered. The last dose of study drug will be the evening dose administered the day before the Week 72 Visit.
7. If the Treatment Period has been extended and the Week 72 CT scan is delayed because of a pulmonary exacerbation ([Section 11.1](#)), subjects should continue to take study drug until the Week 72 CT scan has been completed or the subject enrolls in Study 110. The last dose of study drug for these subjects will be the evening dose administered the day before the CT scan or the evening dose administered before the Day 1 Study 110 Visit, whichever occurs first.

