11 ASSESSMENTS

11.1 Timing of Assessments

The timing of assessments is shown in [Table 3-1](#) and [Table 3-2](#).

[REDACTED] For the remaining assessments, the following assessments must be performed in the following order when more than 1 assessment is required at a particular time point:

[REDACTED]

2. Standard 12-lead ECG recordings
3. Vital signs and pulse oximetry

5. Safety laboratory assessments (i.e., blood draws)

LDCTs [REDACTED] should be performed on the same day. If that is not possible for logistical reasons, LDCT [REDACTED] should be performed within ± 4 days of the scheduled visit. Day 1 LDCTs [REDACTED] must be completed before dosing. The Week 72 CT scan may be delayed for up to 60 days if the subject is recovering from a pulmonary exacerbation. The antibiotic regimen for the treatment of pulmonary exacerbation or infection must be completed at least 28 days before the Week 72 CT scan. If the 28-day antibiotic-free period is not completed before the 60-day extension ends, the subject may roll over into Study 110 and complete the CT scan within the first 30 days of enrolling in Study 110. For subjects who have not completed the 28-day antibiotic-free period after the 60-day extension ends and who choose not to enroll in Study 110, the CT scan should be completed within 1 week of the end of the 60-day extension. The medical monitor should be notified about extensions for the Week 72 CT scan. No extension is permitted for any other assessment. [REDACTED]

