11.5.1.1 Low-Dose Computed Tomography

Inspiratory and expiratory LDCT scans will be obtained at the time points noted in [Table 3-2](#), using a standard low-dose ionizing radiation protocol. CT scans will be obtained using a spirometry-controlled volumetric technique. Additional technique information specific to each manufacturer and model of CT scanner will be provided. Estimated dose for both inspiratory and expiratory scans will total <2.5 mSv combined. Dose calculations will be performed for each CT scanner.

Images will be reconstructed at 5 mm thickness and at <1 mm thickness (exact thickness will be specified for each manufacturer) using a high frequency reconstruction algorithm for 5 mm sections and standard reconstruction for <1 mm sections.

CT scans involve exposure to ionizing radiation. The CT scans used in this research are optimized for low radiation dose and high image quality. While the range of radiation exposure is highly variable, Australians on average are exposed to 1.5 mSv each year from natural sources. No direct evidence of human health effects has been seen in ionizing radiation doses of up to 10 mSv.³⁵ The 2 CT scans used in this study will each use about 2 to 2.5 mSv.

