11.6.2 Clinical Laboratory Assessments

Blood and urine samples will be analyzed at a central laboratory, except for urine pregnancy tests, which will be analyzed at the site. Fasting is not required at any time point. On Day 1, blood samples will be collected before the first dose of the study drug. At all other scheduled visits, these samples will be collected in the order specified in [Section 11.1](#).

Laboratory test results that are abnormal and considered clinically significant will be reported as AEs (see [Section 13.1](#)).

The safety laboratory test panels are shown in [Table 11-1](#).

Table 11-1 Safety Laboratory Test Panels

Serum Chemistry	Hematology	Urinalysis ^a
Glucose	Hemoglobin	Leukocyte esterase
Blood urea nitrogen	Erythrocytes	Nitrite
Creatinine	Mean corpuscular hemoglobin	Urobilinogen
Sodium	Mean corpuscular hemoglobin concentration	Urine protein
Potassium	Mean corpuscular volume	pH
Calcium	Reticulocytes	Urine blood
Chloride	Platelets	Specific gravity
Magnesium	Leukocytes	Urine ketones
Bicarbonate	Differential (absolute and percent):	Urine bilirubin
Inorganic phosphate	Eosinophils	Urine glucose
Total bilirubin, direct bilirubin	Basophils	
Alkaline phosphatase	Neutrophils	
Aspartate aminotransferase	Lymphocytes	
Alanine aminotransferase	Monocytes	
Lactate dehydrogenase	Coagulation Studies	
Gamma-glutamyl transpeptidase	Activated partial thromboplastin time	
Total protein	Prothrombin time	
Albumin	Prothrombin time	
Creatine kinase	International Normalized Ratio	
Amylase		
Lipase		
Vitamin Levels		
Vitamins A, D, E, K, and B12		
Lipid Panel		
Total cholesterol, triglycerides		
Low-density lipoprotein (LDL)		
High-density lipoprotein (HDL)		

^a If urine is positive for leukocyte esterase, nitrite, protein, or blood, microscopic examination of urine will be performed for leukocytes, erythrocytes, crystals, bacteria, and casts.

Pregnancy (β-human chorionic gonadotropin) Tests for Females of Childbearing Potential: Serum samples will be obtained as specified in [Table 3-1](#) and [Table 3-2](#) and analyzed at the central laboratory. Urine pregnancy test kits will be provided by the central laboratory and performed and analyzed at the site as specified in [Table 3-2](#). The urine pregnancy test may be performed on Day 1 and must be negative before the randomization. Tests must also be reviewed and confirmed as negative before each LDCT scan.

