11.6.6 Contraception and Pregnancy

11.6.6.1 Contraception

The effects of VX-661 monotherapy or in combination with ivacaftor on conception, pregnancy, and lactation in humans are not known. Neither VX-661 nor ivacaftor showed any genotoxic potential in a standard battery of in vitro (Ames test, Chinese hamster ovary cell chromosomal aberration) and in vivo (mouse micronucleus) studies. VX-661 and ivacaftor were each found to be nonteratogenic in reproductive toxicology studies in rats and rabbits (see VX-661 and VX-770 Investigator's Brochures). Subjects should follow the contraception requirements outlined in this study protocol. The effects of VX-661 monotherapy or in combination with ivacaftor on the pharmacokinetics (PK) of hormonal contraceptives are not known. Thus, hormonal contraception is not an acceptable method of contraception for female subjects though it is acceptable for the female partners of male subjects.

At this stage in the development of VX-661 in combination with ivacaftor, participation in this study requires a commitment from the research subject and his/her partner to use at least

1 effective method of birth control. Acceptable methods of contraception for participants of this study and their partners are listed below. Methods of contraception should be in successful use from signing of consent, approximately 28 days before the first dose of study drug (unless otherwise noted), and until 90 days following the last dose of study drug.

Contraception for the couple is waived for the following:

- True abstinence for the subject, when this is in line with the preferred and usual lifestyle of the subject. Periodic abstinence (e.g., calendar, ovulation, symptothermal, and postovulation methods) and withdrawal are not acceptable methods of contraception.
- If the male is infertile (e.g., bilateral orchiectomy). Infertility may be documented through examination of a semen specimen or by demonstration of the absence of the vas deferens by ultrasound or medical record before the first dose of the study drug.
- If the female is of non-childbearing potential, per the following:
 - Postmenopausal: spontaneous amenorrhea for at least 12 consecutive months and serum FSH level ≥ 40 mIU/mL at Screening
 - Documented hysterectomy or a bilateral oophorectomy/salpingo-oophorectomy

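### When the Week 72 CT is delayed for an exacerbation, no new pregnancy test is scheduled: the result named for review may be up to 60 days old, or 67 at the latest non-rollover scan

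*Protocol*

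**What the plan says.** Table 3-2 of the protocol places a urine pregnancy test and the second low-dose CT at the Week 72 Visit. Footnote g links them: "Week 72 results will be reviewed before the Low-dose CT scan". The SAP repeats this in footnote g of its Table 10-2. Section 11.6.2 gives the general rule: "Tests must also be reviewed and confirmed as negative before each LDCT scan". It sets no maximum age for the test.

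Section 11.1 normally keeps the CT within 4 days either side of the visit. If the subject is recovering from an exacerbation, the CT may be delayed by up to 60 days, and the antibiotic course "must be completed at least 28 days before the Week 72 CT scan". A subject who is still short of 28 antibiotic-free days when the 60 days end has two routes. With rollover into Study 110, the scan may be done in the first 30 days there. Without rollover, "the CT scan should be completed within 1 week of the end of the 60-day extension". Section 11.1 then says "No extension is permitted for any other assessment", and footnote h of Table 3-2 ends with the same sentence.

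**The concern.** On schedule, the test and the scan belong to one visit, so naming the Week 72 result works as a check close to the scan. The delay rule moves the scan and leaves the test where it was. Nothing visible in the schedule then asks for another test before the scan, so a conception in the intervening weeks need not show in the result that footnote g names.

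What is at stake is fetal radiation exposure in a research scan. Section 11.5.1.1 gives the dose: "The 2 CT scans used in this study will each use about 2 to 2.5 mSv". The protocol chose to put a pregnancy check in front of each scan. In this one pathway its written rules can be followed to the letter and still give a check that is weeks out of date.

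**Working it through.** The plan states no test age, so there is no figure of its own to reproduce. The check is day arithmetic on its windows, with the delay counted from the Week 72 Visit at which the urine test was done.

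**Inputs**
- Week 72 target day: 505 (SAP Appendix B, Table 10-3).
- Normal CT window: 4 days either side of the visit (11.1).
- Maximum delay: 60 days (11.1, footnote h).
- Further time without rollover: 7 days. With rollover: 30 days from enrolment in Study 110 (11.1).
- Antibiotic-free period before the scan: 28 days (11.1).
- Safety Follow-up Visit: 28 ± 7 days after the last dose (8.1.3).
- Last dose when the scan is delayed: the evening before the scan, or before Day 1 of Study 110 (10.2, item 7).

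**Age of the Week 72 result at the scan** (scan day minus test day)
- On schedule, scan at or after the visit: 0 to 4 days.
- End of the extension: 505 + 60 = day 565, so 60 days.
- Latest non-rollover scan: 565 + 7 = day 572, so 67 days.
- Rollover, assuming enrolment on day 60 of the extension: 60 + 30 = 90 days. Study 110 may test at entry, but its schedule is not in these documents, so this figure carries no weight here.

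**How long the gap has to be.** If k days of antibiotics remain at the Week 72 Visit, the 28-day rule makes the result at least k + 28 days old. For illustrative values of k = 7, 14 and 21, that is 35, 42 and 49 days. A gap of several weeks is therefore built in for anyone still on antibiotics at that visit.

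**Does another scheduled test fall in between?**
- The serum test at the Safety Follow-up Visit comes at the earliest 28 − 7 = 21 days after the last dose. The last dose is normally the evening before the scan, so this test follows the scan. Even if dosing ended on day 60 of the extension, the earliest date is 60 + 21 = day 81, after the day-67 scan.
- The serum test at the Early Termination of Treatment Visit applies only to premature discontinuation (8.1.4).
- No other test is scheduled after Week 72.

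**Sensitivity.** If the Week 72 Visit took place 7 days early and the 60 days ran from the nominal date, the ages would be 60 + 7 = 67 and 67 + 7 = 74 days.

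**Number of subjects.** The documents do not give it. Under assumed inputs only, with 40% to 60% of the 40 subjects being females of childbearing potential and 5% to 25% of these needing a delay:
- low: 40 × 0.40 × 0.05 = 0.8
- middle, at 50% and 15%: 40 × 0.50 × 0.15 = 3.0
- high: 40 × 0.60 × 0.25 = 6.0

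These count delayed scans in such subjects, not pregnancies missed.

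**With the fix**, the result is 0 to 4 days old at any scan.

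**The case against.** The strongest reply is that 11.6.2 already covers this. Its duty is mandatory and attaches to each scan, not to a visit, so a careful site may well read it as calling for a fresh test. The same section allows additional laboratory evaluations when clinically appropriate. The sentence about extensions bars late windows for other assessments; it does not forbid a repeat. Because the CT window also runs 4 days before the visit, footnote g can be met for an early scan only if the test is done at or before that scan, which suggests that the test was meant to accompany it. The medical monitor should also be told of each CT extension.

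Much of this stands. A reader might infer that the safeguard is lost or that sites may not retest. The documents do not support that: a fresh test is permitted. What remains is that the repeat is left to discretion, while footnote g points to a specific and possibly old result.

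A reader might also add that these subjects keep taking study drug, since "subjects should continue to take study drug until the Week 72 CT scan has been completed or the subject enrolls in Study 110". That does not strengthen the point. From Week 12 the scheduled tests on drug are 12 weeks apart, which is 84 days, so 60 or 67 days without a test is within what the protocol accepts for dosing.

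The risk is also limited. Although "hormonal contraception is not an acceptable method of contraception for female subjects", section 11.6.6.1 requires at least one effective method until 90 days after the last dose (with waivers such as true abstinence) and does not require hormonal methods to be stopped. Section 11.5.1.1 states that no direct evidence of human health effects has been seen up to 10 mSv. These facts make harm unlikely, but they do not explain why the check should be weaker for a delayed scan than for one on time.

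Finally, text directly after the extension sentence in 11.1 is redacted, and the SAP copy of footnote h is redacted before that sentence. The reading that no exception exists rests on protocol footnote h, which shows none.

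**Conclusion.** The point holds as a scheduling gap of limited scope. For a delayed Week 72 CT the schedule requires no new pregnancy test, and the result it names may be up to 60 days old, or 67 at the latest non-rollover scan. Both figures assume that the delay is counted from the visit at which the test was done.

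It is a subject-protection matter about radiation only, for a small number of females of childbearing potential that the documents do not state. It does not affect the primary endpoint, its analysis or the Week 72 safety data. It is an optional improvement, worth making because the remedy costs almost nothing.

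**What to change.** In footnote g of protocol Table 3-2, and in its copy in SAP Table 10-2, replace the sentence on the Week 72 result with: *For the Week 72 CT, a urine pregnancy test is done on the day of the scan or within 4 days before it, and is reviewed before the scan. If the CT is delayed, the test is repeated. For a subject who has entered Study 110, a test done in that study within the same 4 days may be used.*

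In section 11.1 and footnote h, add to the sentence on extensions: *, except that the urine pregnancy test is repeated before a delayed CT.*

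The cost is one urine test per affected subject, normally at a CT attendance already planned, with kits that 11.6.2 already supplies for reading at the site. No blood draw or change to any analysis is needed, and a test on the day of the scan adds no visit. The wording change needs the approvals and regulatory submission set out in protocol section 13.2.3, so it could be carried in the next amendment, with a note to sites until then.

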11.1.1 Informed Consent/Assent

Each subject of age of consent (per local requirements) must sign and date a study-specific ICF before any study-specific procedures can be performed. Subjects not of age of consent must assent, if applicable per local requirements, to participate in the study, and the subject's parent or legal guardian must sign and date a study-specific ICF before any study-specific procedures can be performed. The consent forms will comply with all applicable regulations governing the protection of human subjects. An ICF and Assent Form, approved by Vertex and the site's IRB or IEC, must be used.

11.1.2 Assigning Subject Number

Once a subject has signed an ICF or assent, if applicable, a subject number will be assigned. The subject will retain this number for the entire study. Detailed instructions on assigning subject numbers will be provided in the Study Reference Manual. If a subject is rescreened, the subject retains the original subject number.

11.2 Subject and Disease Characteristics

Subject and disease characteristics include the following: demographics, medical history, height, weight, and sweat chloride.

Medical history will be elicited from each subject during screening. Based on the medical history, the subject will be assessed for any disqualifying medical conditions as specified in the inclusion and exclusion criteria. The medical history shall include a complete review of systems, past medical and surgical histories, and any allergies.

Sputum microbiology, as documented in the subject's medical record over the past 2 years, will be collected during screening.

A sweat chloride test must be performed at the Screening Visit if an eligible sweat chloride value is not available in the subject's medical records and the Screening Visit value is needed to establish eligibility. For subjects using sweat chloride values documented in their medical records to establish eligibility, the sweat chloride test at the Screening Visit is optional. Collection of sweat samples will be performed using an approved collection device. Sweat samples will be sent to a central laboratory for testing and interpretation of results. Specific instructions for collection, handling, processing, and shipping of sweat chloride samples to the central laboratory will be provided separately.

11.3 Pharmacokinetics

Not applicable

11.4 Pharmacodynamics

Not applicable

11.5 Efficacy

11.5.1 Chest Imaging

[figure not shown]
Chest imaging, as performed by LDCT [REDACTED] has the potential to reveal structural CF pulmonary disease even when a patient has normal spirometric function. As such, this study will explore the effect of VX-661/ivacaftor treatment on endpoints obtained through chest imaging.

11.5.1.1 Low-Dose Computed Tomography

Inspiratory and expiratory LDCT scans will be obtained at the time points noted in [Table 3-2](#), using a standard low-dose ionizing radiation protocol. CT scans will be obtained using a spirometry-controlled volumetric technique. Additional technique information specific to each manufacturer and model of CT scanner will be provided. Estimated dose for both inspiratory and expiratory scans will total <2.5 mSv combined. Dose calculations will be performed for each CT scanner.

Images will be reconstructed at 5 mm thickness and at <1 mm thickness (exact thickness will be specified for each manufacturer) using a high frequency reconstruction algorithm for 5 mm sections and standard reconstruction for <1 mm sections.

CT scans involve exposure to ionizing radiation. The CT scans used in this research are optimized for low radiation dose and high image quality. While the range of radiation exposure is highly variable, Australians on average are exposed to 1.5 mSv each year from natural sources. No direct evidence of human health effects has been seen in ionizing radiation doses of up to 10 mSv.³⁵ The 2 CT scans used in this study will each use about 2 to 2.5 mSv.

11.5.1.3 Imaging Scoring

All CT [redacted] scans will be evaluated by centralized expert readers using the Brody/CF-CT scoring system.

[figure not shown]
- The Brody/CF-CT scoring system semiquantitatively scores the degree of structural lung disease as shown on CT in patients with CF. It has been extensively tested and

validated (see [Section 8.2.3](#)). This score provides both localization and quantification of 5 abnormalities characteristic of CF lung disease: bronchiectasis, air trapping, mucous plugging, bronchial wall thickening, and parenchymal changes (includes parenchymal opacities, ground glass opacities, and cysts/bullae).

- Scores from other scoring algorithms for measuring the features of the Brody CF-CT scoring systems, as well as other features associated with structural lung disease, may be assessed.

11.6 Safety

Safety evaluations will include AEs, clinical laboratory assessments, and clinical evaluation of vital signs, pulse oximetry, ECGs, and PEs.

